After 24 intervention sessions, patients are invited for the post-intervention assessment. This assessment will be scheduled as close as possible to the last training session. Participants will first evaluate the intervention with a non-blinded study member. Directly afterwards, participants will undergo a post-intervention assessment ('T1'). This assessment comprises a neuropsychological assessment and questionnaires (see Table 2). One team member (TB) will be de-blinded after the last T1 visit. All assessments after baseline will make use of parallel versions of neuropsychological tasks, if possible.

After six months ('T2'), one year ('T3') and two years ('T4'), participants will again undergo an extensive neuropsychological assessment and questionnaires. At T3 and T4, motor symptoms will also be assessed. From T3 onwards will be a naturalistic follow-up.

Blinding

Outcome assessors will be blinded for the full length of their role as assessor, while non-blinded team members will not assess participants at any point in this study. Blinded study members will not have access to the key of the randomization. Trial participants will be blinded for the full length of the study. Participants will be asked not to share any details of their intervention with the outcome assessor at any point in the study. When the participants' condition is revealed to an outcome assessor, he or she will be replaced by another assessor for this participant.

Drop-outs

Participants that drop out of the study after being allocated to an intervention condition will not be replaced. We expect a low drop-out rate on the basis of our pilot study (one drop-out in 21 participants) and the low burden and short duration of both training conditions. In our sample size calculation, we conservatively account for 10% drop-out.

In case a participant withdraws from the study after four weeks of training (or more), we will aim to schedule an exit-measurement to measure the intervention effect.

Medication adjustments

Participants and their neurologist will be requested to retain a stable medication regime during the study period, specifically during the intervention. Patients and their neurologist will be requested to inform the study team if medication changes are clinically necessary.

Table 2 Tabular overview of the study time schedule including assessments and visits.

Time-point	T-2	T-1	T0	T1	T2	T3	T4
Pre-screening							
Informed consent for pre-screening		X					
SAGE	X						

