An active control condition is used to correct for the nonspecific cognitive activity that participants in the CT group go through. In the control condition, participants undergo cognitive engagement using three games (i.e. solitaire, trivia questions and hangman) with a total duration of 45 minutes that will sequentially be performed and are hypothesized not to train specific cognitive functions.

Outcomes

Primary outcome

The primary outcome is the efficacy of CT on executive functions, measured by the percentage correct change score on a previously used computerized self-paced version of the Tower of London (ToL) task [29]. The ToL measures several aspects of executive functions, including planning, inhibition, and working memory [61]. This neuropsychological task consists of a model of three pins with different lengths, and three differently colored beads. In this task, the goal is to get from a starting position to a target position in as minimal steps as possible. There are five planning conditions that range in difficulty, with possible solutions ranging from one to five steps (i.e. task-load S1-S5). After nine exercise items with feedback, 100 pseudo-randomized test trials will be presented with a maximum response duration of 45 seconds per trial and no feedback on accuracy.

Secondary outcomes

The secondary outcome measures include (i) subjective cognitive complaints, (ii) cognitive function (other than the ToL) and (iii) structural and functional connectivity and brain network characteristics. All outcomes described below are changes after intervention relative to baseline.

- 1) Subjective cognitive dysfunction change after the intervention will be measured by the Parkinson's Disease Cognitive Functional Rating Scale (PD-CFRS, [62]) score and the Cognitive Failures Questionnaire (CFQ) score at the end of the intervention (T1), and at follow-up (T2, T3, and T4). We use the PD-CFRS questionnaire as a Parkinson-specific and sensitive measurement of subjective cognitive function. This questionnaire will be filled out by the participant and if possible by a caregiver. We will additionally use the CFQ as this measure has been used more frequently and it is more sensitive to small cognitive errors in daily living such as memory problems, absent-mindedness and slips of action[63];
- 2) Cognitive function change after the intervention will be measured by

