- Data on physical activity at each visit will be measured by the New Zealand Physical Activity Questionnaire – Short Form, a structured interview on mild, moderate and vigorous physical activity, as physical activity is known to positively influence cognitive function and potentially provide a neuroprotective effect.[69, 70];
- We will rate motor symptom severity by the Unified Parkinson's Disease – Rating Scale part III and assess disease stage by the modified Hoehn & Yahr stage [71];
- Medication usage data are collected and transformed into a 'levodopa equivalent daily dosage' [33]. Dopamine replacement therapy may influence cognitive functions [72, 73];
- Intervention compliance will automatically be monitored by the training module. We will calculate total compliance as the proportion of completed training games out of 24 total sessions: $[N_{\text{completed}} / N_{\text{total}}] \times 100\%$, in which N_{total} is 13 games x 24 sessions in the CT

condition, and 3 games x 24 sessions in the AC condition. We define non-compliance as a completion rate lower than 75%, in accordance with Petrelli and colleagues [74].

ANALYSIS PLAN

Data-analyses will be performed on the Modified-Intention-To-Treat population, which comprises the compliant participants that underwent at least 75% of the intervention and at least one post-training assessment. We will compare the baseline characteristics of this sample to the Intention-to-Treat population (all randomized subjects). Secondary Per Protocol-analyses will be performed comprising the population that underwent the complete study protocol. Analyses will be performed with IBM SPSS version 22 (Armonk, NY, USA) and in R [75]. We will employ a statistical threshold of $\alpha = .05$.

The primary outcome will be analyzed using a multivariate mixed-model analysis using the accuracy on the five separate task-loadings (S1-S5) of the ToL at post-training visit (T1) as dependent measures, the training condition (CT vs. AC) as independent measure and baseline score of the outcome measures as covariates. We will construct a separate adjusted model with age, sex and years of education as additional covariates of no-interest. No imputation of missing values will be performed as this is not needed in linear mixed models.

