We will perform Fisher's exact tests to verify if the demographic and clinical characteristics of the MRI subsample are similar to those of the full study sample. Functional MRI and diffusion tensor imaging data will be (pre)processed and analyzed with Statistical Parametric Mapping (SPM) software, FMRIB Software Library (FSL) and in-house Matlab (The MathWorks, Inc, Natick, MA, USA), scripts in combination with open-source toolboxes for (dynamic) network analysis [67, 68] to study the effects of cognitive training on the functional and structural brain network, respectively. We will also employ typical independent component analysis in combination with dual regression for resting-state functional connectivity and morphometric (e.g. cortical thickness) analysis on T1-weighted structural MRI to study within and between group-effects of our intervention. Moreover, to establish treatment response at the individual level, Multivariate Pattern classification ('machine learning') analyses will be performed to identify predictive markers (clinical, neuropsychological and neuroimaging) to be able to predict (in future patients) who is most likely to benefit from cognitive training.

Sample size

The sample size calculation is performed on the basis of a previous meta-analysis on the effects of CT on cognitive function [22]. This study showed an effect size of Hedges $g = .23$ (i.e. $f = .12$), based on the effect of CT on improving *global* cognitive function. The sample size needed to detect this effect is 112, based on a repeated-measures analysis of variance, corrected for a moderate correlation between pre- and post-treatment measures (i.e. $r \approx .6$). This sample size estimation also provides a good indicator for the power of our multivariate mixed-model regression analysis with adjustment for baseline measures.

To ensure adequate power for the secondary study parameters, i.e. the development of PD-MCI and PD-D at one and two years follow-up, with an $\alpha = .05$ and $\beta = .8$, and based on a small drop-out ($\sim 10\%$) given the home-based, easily-accessible training, we will include 140 participants.

References

1. Jankovic J: **Parkinson's disease: clinical features and diagnosis.** *Journal of neurology, neurosurgery, and psychiatry* 2008, **79**:368-376.

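### The 112 patients said to detect g = .23 in fact detect about 0.48 SD between arms; for 0.23 SD a single-score analysis has about 36% power with 126 evaluable

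*Combined protocol and SAP*

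**What the plan says.** The Sample size section takes its effect from a meta-analysis of cognitive training on global cognition, given as "Hedges $g = .23$ (i.e. $f = .12". It continues: "The sample size needed to detect this effect is 112, based on a repeated-measures analysis of variance, corrected for a moderate correlation". The correlation in question is that of baseline with follow-up scores, put at about .6. The section does not say which F-test of the repeated-measures ANOVA is meant, and it attaches no power target to the 112.

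It then carries the figure over to the planned analysis: "This sample size estimation also provides a good indicator for the power of our multivariate mixed-model regression analysis with adjustment for baseline measures". Enrolment is set at 140, justified by the secondary conversion endpoints "with an $\alpha = .05$ and $\beta = .8" and by about 10% drop-out. The Drop-outs section says: "In our sample size calculation, we conservatively account for 10% drop-out".

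Under Primary outcome, efficacy is "measured by the percentage correct change score on a previously used computerized self-paced version of the Tower of London (ToL) task". The Analysis plan specifies a "multivariate mixed-model analysis using the accuracy on the five separate task-loadings (S1-S5) of the ToL at post-training visit (T1) as dependent measures", with training condition as the factor and baseline scores as covariates. The primary analysis set "comprises the compliant participants that underwent at least 75% of the intervention and at least one post-training assessment".

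**The concern.** Setting f = g/2 is right for two independent groups measured once. In a two-arm, two-time-point repeated-measures ANOVA the treatment effect is the group-by-time interaction, and f for that term is on a different scale. Entering g/2 there doubles the effect being powered.

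This is the only quantitative power argument in the plan. A reader who trusts it will think the trial had a good chance of finding the meta-analytic effect, and may take a non-significant primary result as evidence against an effect of that size. If the figure is wrong, that reading is not supported.

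**Working it through.** **Inputs.** From the Sample size section: g = .23, f = .12, r = .6, N = 112, enrolment 140. From the Drop-outs section: 10% drop-out, so 140 x 0.9 = 126 evaluable. From the Analysis plan: alpha .05. Assumed: two-sided test, 80% power as the target for 112, and g expressed as a between-arm difference in units of the between-patient SD of one score.

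**1. Reproducing 112.** For the within-subject or interaction term with two time points, lambda = f² x N x 2/(1 − r), with F on (1, N − 2) df.
- f = .12, N = 112: lambda = .0144 x 112 x 2/.4 = 8.064; power 80.4%.
- N = 110: power 79.6%.

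So 112 is the smallest even N that reaches 80%.

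**2. What f = .12 means on that scale.** Suppose the arms are equal at baseline and differ by d SD after training. The four cell means are 0, 0, 0 and d, and each interaction deviation is ± d/4. Hence f = d/4, and f = .12 is d = 4 x .12 = 0.48 SD. Cross-check with a change-score test: the variance of change is 2(1 − .6) = .8, so lambda = d² x N/(4 x .8) = .2304 x 112/3.2 = 8.064, the same value and the same 80.4%. A difference of 0.23 SD is f = .23/4 = .0575.

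**3. Other routes to 112.**

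| Reading | N for 80% |
|---|---|
| Interaction, unrounded f = .115 (0.46 SD) | 122 (77.0% at 112) |
| Between-group repeated-measures test, f = .12, lambda = f² x N x 2/(1 + r) | 438 |
| Single time point, f = .12, lambda = f² x N | 548 |

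A time-only effect also gives 112, but it does not compare the arms. Rounding explains little of the gap.

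**4. Power for 0.23 SD on one score, r = .6.** The baseline-adjusted comparison has residual SD sqrt(1 − .36) = .8, so the standardised effect is .23/.8 = .2875, with N − 3 df. At 126 the noncentrality is .2875 x sqrt(126)/2 = 1.61.

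| N | Interaction or change score | Baseline-adjusted | Detectable with 80%, baseline-adjusted | 95% CI half-width |
|---|---|---|---|---|
| 112 | 27% | 33% | 0.43 SD | 0.30 SD |
| 126 | 30% | 36% | 0.40 SD | 0.28 SD |
| 140 | 33% | 39% | 0.38 SD | 0.27 SD |
| N for 80% | 478 | 382 | | |

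For 0.48 SD at 112 the baseline-adjusted test has 88% power, against 80.4% for the ANOVA. Moving from the ANOVA to the baseline-adjusted model is therefore not the problem; the conversion of g to f is.

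**5. Sensitivity at 126.** For r = .5 to .7, power is 32% to 43% and the detectable effect 0.44 to 0.36 SD. The documents give no rate for completion below 75%. If a further 5% to 20% of the 126 were excluded (assumed), 120 to 101 would remain, with 35% to 30% power.

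**6. Five task loads.** Joint-model power needs inter-load correlations and per-load effects that the documents do not give. Assume 0.23 SD on every load and a common inter-load correlation c. The mean of the five loads then has SD sqrt((1 + 4c)/5). At 126 and r = .6, a common-effect test has 45%, 54%, 67% and 86% power for c = .7, .5, .3 and .1. A 5-df omnibus test has 24%, 30%, 41% and 62%. Over N = 112 to 140, r = .5 to .7 and c = .1 to .7, the omnibus test peaks at 78.5%.

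**The case against.** The strongest objection is scope. The planned primary model is multivariate over five loads, and with 0.23 SD on every load some favourable combinations pass 80%: at N = 112, 81.3% with r = .6 and c = .1, and 80.4% with r = .7 and c = .2. This stands as a limit on the 36%, which is a single-score figure. It does not rescue the 112. The plan derives that number from a repeated-measures ANOVA, not from a five-load argument, and at c = .1 an effect of 0.23 SD per load is already .23/sqrt(1.4/5), about 0.43 SD, on the load average.

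Second, the F-test, the 80% target and the units of g are inferred. That is correct. The match at 112 makes the first two likely, and the Background says the meta-analysis pooled randomised controlled trials, which supports a between-arm reading of g. The plan does not document any of the three.

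Third, 140 is justified by the conversion endpoints and drop-out: 112/0.9 is about 125, so 140 does not follow from 112 alone. The 0.40 SD is thus a back-calculation from the planned enrolment, not a target that the plan states.

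Fourth, a larger executive effect may have been expected: g = .23 is for global cognition, and the Interventions section reports a medium-sized pilot effect without a number. At 0.48 SD, single-score power at 126 would be 92%. But the plan does not size the trial on that effect.

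**Conclusion.** The concern holds. On the plan's own inputs, the repeated-measures ANOVA with 112 patients has 80% power for about 0.48 SD between arms, not 0.23 SD. For 0.23 SD it has 27%. The baseline-adjusted single-score comparison has about 36% at 126 evaluable, and the effect it can detect with 80% power there is about 0.40 SD, or 0.40/0.23 = 1.7 times the cited g.

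This rests on a two-sided .05 test, r = .6, an inferred 80% target, and g in between-patient SD units. Confidence is high for the single-score arithmetic; power of the joint five-load model remains unknown. The treatment estimate is not biased. With a confidence interval half-width of about 0.28 SD at 126, a non-significant result need not exclude 0.23 SD: if the true effect were zero, only about 35% of non-significant trials would have an upper limit below 0.23.

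**What to change.** Change the wording of the Sample size section:

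- Replace the claim that 112 detects g = .23 with, for example: 'Assuming 126 of 140 evaluable (10% drop-out, before any exclusion for non-compliance), a single-score baseline-adjusted comparison (r = .6, two-sided .05) has 80% power for about 0.40 SD and about 36% for 0.23 SD.'
- Tie the sentence on the multivariate mixed model to this figure as a single-score approximation, and say that power of the joint five-load model was not computed.
- Add: 'A non-significant primary result may not exclude 0.23 SD; this will be judged by the 95% confidence interval.'
- Correct beta = .8 to power .8 (beta = .2).
- If a larger executive-function effect was the intended target, name it and its basis in place of g = .23.

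The cost is text only: enrolment, estimator and analysis set stay as they are, and the stated power becomes less favourable. The documents do not give recruitment status (the last amendment was approved in October 2020). If recruitment has closed, the correction serves interpretation rather than design.

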Appendix 1 - MRI parameters

All scans were acquired on a Discovery* MR750 3.0T MRI scanner (General Electric, Milwaukee) with a 32-channel head coil at the Amsterdam UMC, VU University (Amsterdam, the Netherlands).

Resting-state fMRI: 272 volumes (~10 minutes) of T2*-weighted echo-planar images (EPI's) with the following parameters: TR = 2200 ms, TE = 28 ms, flip angle = 80°, 42 axial slices (3.3 x 3.3 x 3.3 mm, matrix size 64 x 64). Sequential ascending acquisition according the hypophysis – fastigium (HYFA) line. High-order shimming (HOS) was performed to compensate for inhomogeneity in the magnetic field. Two reference scans in opposite phase-encode directions are acquired prior to the resting-state acquisition to correct for susceptibility induced distortions during post-processing: TR = 8000 ms, TE = 60 ms. The field-of-view, position, orientation and matrix dimensions are identical to the resting-state scan.

Diffusion-weighted MRI: Single Spin Echo multi-shell DWI with 73 diffusion weighted images (25 x b = 1000 s/mm², 24 x b = 2000 s/mm², 24 x b = 3000 s/mm²) and seven non-diffusion weighted (b = 0 s/mm²). TR = shortest (6000-7000 ms), TE = shortest (80-90 ms), 56 axial slices (2.5 x 2.5 x 2.5 mm, matrix size 128 x 128). Interleaved ascending acquisition according the hypophysis – fastigium (HYFA) line. High-order shimming (HOS) was performed to compensate for inhomogeneity in the magnetic field. Two reference scans in opposite phase-encode directions are acquired prior to the diffusion-weighted image to correct for susceptibility induced distortions during post-processing: TR = 8000 ms, TE = 60 ms. The field-of-view, position, orientation and matrix dimensions are identical to the diffusion-weighted image

Structural MRI: 3D sagittal MP-RAGE T1-weighted sequence according to ADNI-3 protocol with the following parameters: TI = 900 ms, TE = min full echo, flip angle = 8°, 168 slices (1 x 1 x 1 mm, matrix size 256 x 256). 3D Cube sagittal Phase sensitive inversion recovery (PSIR) with the following parameters: TI = 650 ms, TR = 3000 ms, TE = minimum, 168 slices (1 x 1 x 1 mm, matrix size 256 x 256).
